3.3 DOSE MODIFICATIONS

3.3.1 Overdose

There is no specific experience in the management of ibrutinib overdose in participants. Subjects who ingest more than the recommended dosage should be closely monitored and given appropriate supportive treatment.

3.3.2 Dose Modification for Adverse Reaction

Dose reductions will be required for any of the following toxicities:

- Grade 3 ANC (< 1,000/ μ L) with an associated temperature $\geq 38.5^{\circ}\text{C}$
- Grade 4 ANC (< 500/ μ L) for more than 7 days
- Grade 3 thrombocytopenia (< 50,000/ μ L) in the presence of clinically significant bleeding events
- Grade 4 thrombocytopenia (< 25,000/ μ L)
- Grade 3 or 4 nausea, vomiting, or diarrhea despite optimal anti-emetic and/or anti-diarrheal therapy

- Any other Grade 4 or unmanageable Grade 3 toxicity attributed to ibrutinib
- Optional dose reduction can be done also at investigator discretion for any bothersome toxicity

Recommended Dosage Modifications for Adverse Reactions		
Adverse Reaction	Occurrence	Dose Modification after Recovery
Grade 2 cardiac failure	First	Restart at 280 mg daily ^a
	Second	Restart at 140 mg daily ^a
	Third	Discontinue Ibrutinib
Grade 3 cardiac arrhythmias	First	Restart at 280 mg daily ^a
	Second	Discontinue Ibrutinib
Grade 3 or 4 cardiac failure	First	Discontinue Ibrutinib
Grade 4 cardiac arrhythmias		
Other Grade 3 or 4 non-hematological toxicities ^b Grade 3 or 4 neutropenia with infection or fever Grade 4 hematological toxicities	First	Restart at 280 mg daily
	Second	Restart at 140 mg daily
	Third	Discontinue Ibrutinib

^a Evaluate the benefit-risk before resuming treatment

^b For Grade 4 non-hematologic toxicities, evaluate the benefit-risk before resuming treatment

If the dose of ibrutinib is reduced, at the investigator's discretion, the dose of ibrutinib may be re-escalated after 4 weeks of a dose reduction in the absence of a recurrence of the toxicity that led to the reduction.

3.3.2.1 Ibrutinib Dose Modifications – General:

Occurrence	Action to be taken
Hematologic Adverse Events	
First	Withhold ibrutinib until recovery to Grade ≤ 1 or baseline; may restart at the original dose level
Second	Withhold ibrutinib until recovery to Grade ≤ 1 or baseline; may restart at 1 dose level below that for which the toxicity occurs (i.e., 280 mg/day for 420 mg/day dose)

Occurrence	Action to be taken
Third	Withhold ibrutinib until recovery to Grade ≤ 1 or baseline; may restart at 1 dose level below that for which the toxicity occurs (i.e., 140 mg/day for 280 mg/day dose)
Fourth	Discontinue ibrutinib
Non-Hematological Adverse Events	
First	Withhold ibrutinib until recovery to Grade ≤ 1 or baseline; may restart at original dose level
Second	Withhold ibrutinib until recovery to Grade ≤ 1 or baseline; may restart at 1 dose level below that for which the toxicity occurs
Third	Withhold ibrutinib until recovery to Grade ≤ 1 or baseline; may restart at 1 dose level below that for which the toxicity occurs
Fourth	Discontinue ibrutinib

3.3.2.2 Dose modification for atrial fibrillation:

For Grade 3 or 4 atrial fibrillation or persistent atrial fibrillation of any grade, consider the risks and benefits of ibrutinib treatment. If clinically indicated, the use of anticoagulants or antiplatelet agents may be considered for the thromboprophylaxis of atrial fibrillation.

3.3.2.3 Dose modifications for hepatic impaired subjects:

- Ibrutinib is metabolized in the liver and therefore subjects with clinically significant chronic hepatic impairment at the time of Screening (Child- Pugh class C) are excluded from study participation. Refer to [Appendix J](#) for Child-Pugh classification. For subjects with a direct bilirubin $> 3 \times$ ULN (Grade 3 CTCAE), ibrutinib will be held until the bilirubin returns to $\leq 1.5 \times$ ULN (Grade 1 CTCAE) or baseline. Upon reduction to $\leq 1.5 \times$ ULN ibrutinib will be re-started at one dose level below that for which the toxicity occurs (see [Table 1](#) for dose modification schedule).
- For subjects whose baseline AST/ALT is $\leq 3 \times$ ULN, if ALT or AST increases to $> 5 \times$ ULN (Grade 3 CTCAE) ibrutinib will be held until the ALT/AST value returns to $\leq 3 \times$ ULN (Grade 1 CTCAE) or baseline. Ibrutinib will be re-started at one dose level below that for which the toxicity occurs.
- For subjects whose baseline AST/ALT is between 3 to 5 \times ULN (because of chronic GvHD), if ALT/AST increases to 1.5 \times baseline level then ibrutinib will be held until the ALT/AST value returns to $\leq 3 \times$ ULN or baseline. Ibrutinib will be re-started at one dose level below that for which the toxicity occurs.

Table 1: Ibrutinib Dose Modifications for Hepatic Impairment

Occurrence	Action to be Taken
------------	--------------------

First	Withhold study drug until recovery to Grade ≤ 1 CTCAE or baseline; restart at 1 dose level below that for which the toxicity occurs (280 mg/day for 420 mg/day dose)
Second	Withhold study drug until recovery to Grade ≤ 1 CTCAE or baseline; restart at 1 dose level below that for which the toxicity occurs 140 mg/day for 280 mg/day dose)
Third	Discontinue study drug

Treatment with ibrutinib will be discontinued if because of unacceptable toxicity the subject has missed drug for more than a total of 28 days in the first six months of the study.

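### The table in section 3.3.2 and the general schedule in 3.3.2.1 give different restart doses and stopping points for the same events, and nothing says which governs

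*Combined protocol and SAP*

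**What the plan says.** Section 3.3.2 and its subsections hold four sets of instructions that bear on the same events.

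- **The list**, under "Dose reductions will be required for any of the following toxicities". It includes Grade 4 thrombocytopenia, Grade 3 thrombocytopenia "in the presence of clinically significant bleeding events", and "Any other Grade 4 or unmanageable Grade 3 toxicity attributed to ibrutinib". It names no restart dose and no point at which treatment ends. It closes with "Optional dose reduction can be done also at investigator discretion for any bothersome toxicity".
- **The table**, headed "Recommended Dosage Modifications for Adverse Reactions". Its last row covers "Other Grade 3 or 4 non-hematological toxicities", Grade 3 or 4 neutropenia with infection or fever, and "Grade 4 hematological toxicities". The steps are 280 mg, 140 mg, then discontinuation at the third occurrence. A cardiac row ends treatment at the first occurrence of Grade 3 or 4 cardiac failure or "Grade 4 cardiac arrhythmias". Grade 3 arrhythmia restarts once at 280 mg and stops at the second occurrence.
- **Section 3.3.2.1 (general).** It covers all hematologic and all non-hematological adverse events, with no grade limit. After recovery to Grade 1 or baseline it permits the original dose first, then one level lower after each of the second and third events. It discontinues at the fourth.
- **Section 3.3.2.2.** For Grade 3 or 4 atrial fibrillation, or persistent atrial fibrillation of any grade, it asks the investigator to weigh risks and benefits. It gives no dose step and no stop.

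Section 3.2.1 separately sets lower starting doses with certain azoles: 280 mg with voriconazole or lower-dose posaconazole, and 140 mg with higher-dose posaconazole.

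**The concern.** An investigator facing a severe toxicity needs one restart dose and one stopping point. Here the answer depends on which schedule is consulted. Section 1.2.2.4.5 notes fatal cardiac events among ibrutinib-treated subjects and sends investigators to the dose modification guidelines, but those guidelines do not agree with each other.

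At stake are participant safety and consistent dosing across sites. A participant could return to full dose, or stay on drug, where the table would reduce or end treatment. Section 8.7 defines a deviation as non-compliance with the protocol. With unranked rules, two sites can treat the same event differently and neither is clearly deviating.

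**Working it through.** No sample-size or power figure enters this point. The check sets the rules side by side for the same event and then looks for a sentence that ranks them.

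**Step 1. Participant on 420 mg, event in the table's last row.**

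| Occurrence | Table, 3.3.2 | 3.3.2.1 permits | Difference |
|---|---|---|---|
| First | 280 mg | 420 mg | 420 − 280 = 140 mg |
| Second | 140 mg | 280 mg | 280 − 140 = 140 mg |
| Third | stop | 140 mg | 140 − 0 = 140 mg |
| Fourth | already stopped | stop | one occurrence later |

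At the first event the difference is 140/420 = 33% of the full dose. It can be short-lived, since section 3.3.2 allows re-escalation after 4 weeks at a reduced dose if the toxicity has not recurred.

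**Step 2. What the list settles.** Where an event is on the list, such as Grade 4 thrombocytopenia, a mandatory reduction most naturally outranks a permission to restart at the original dose. That settles the direction of the first step. It does not settle third against fourth, because the list has no stopping rule. Where an event is in the table but not on the list, such as a manageable Grade 3 non-hematological toxicity other than the listed GI events, both restart dose and stopping point stay open.

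**Step 3. Cardiac events.**

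| Event | Table | 3.3.2.1 | 3.3.2.2, if atrial fibrillation |
|---|---|---|---|
| Grade 3 or 4 cardiac failure | stop at first | original dose permitted at first; stop at fourth | not applicable |
| Grade 4 arrhythmia | stop at first | same | risk-benefit judgment only |
| Grade 3 arrhythmia, first | 280 mg after benefit-risk evaluation | original dose permitted | risk-benefit judgment; compatible with the table |
| Grade 3 arrhythmia, second | stop | one level lower | risk-benefit judgment only |

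**Step 4. Participants who start below 420 mg (section 3.2.1).** The table gives absolute doses.

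- Start at 280 mg: first restart 280 mg, and 280 − 280 = 0, so no reduction.
- Start at 140 mg: first restart 280 mg, and 280/140 = 2, a doubling after a severe toxicity.

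Section 3.3.2.1 and the hepatic schedule (Table 1 in 3.3.2.3) word their steps as one level below the dose at which the event occurred. But 140 mg is the lowest level in the protocol, and 3.3.2.1 does not say what a further reduction from there means.

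**Step 5. A ranking sentence.** None appears in sections 3.3.2 to 3.3.2.3. Section 1.2.2.4.5 refers to the guidelines without naming a schedule, and the removal criteria in 3.8.1 repeat none of the table's stops.

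**The case against.** The best defense is that 3.3.2.1 is labelled general and its restarts are permissive, so the specific table governs by ordinary reading. An investigator who follows the table's restart doses from 420 mg does not breach 3.3.2.1's restart steps. Other safeguards exist: weekly team review (7.5.1), a limit of 28 days of drug missed for toxicity in the first six months (end of 3.3.2.3), and removal at the principal investigator's discretion (3.8.1).

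Part of this stands: nobody is compelled to give a higher dose. But the fallback reading is not written down. Section 3.3.2.1 has no grade limit, the table is itself only recommended, and the table has its own catch-all row that competes with the general schedule. The discontinuation at the fourth event is not worded as a permission, and it differs from the table's third.

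A reader might infer more than the documents support:

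- *That a bleeding participant with Grade 3 thrombocytopenia may return to 420 mg.* The list requires a reduction, and that mandatory wording settles the case.
- *That the list orders a reduction where the table orders a stop for Grade 4 cardiac events.* Read as a minimum, the list does not bar stopping.
- *That 3.3.2.2 contradicts the table for all atrial fibrillation.* For a first Grade 3 event the table's own footnote asks for a benefit-risk evaluation. The conflict is confined to Grade 4 and to a second Grade 3 event.

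**Conclusion.** The conflict between the table and 3.3.2.1 is real and can be confirmed from section 3.3.2 alone. For a participant on 420 mg with an event in the table's last row, it amounts to one dose level (140 mg) at each step and one occurrence before stopping. For Grade 3 or 4 cardiac failure and Grade 4 arrhythmia, it is a stop at the first event against permission to restart at the original dose. The absolute restart doses are a separate defect in the same table, and they matter more if the table is made to govern.

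No frequency can be put on this. The 42-patient steroid-refractory study in section 1.2.2.3 reports Grade 3 or higher pneumonia (6), fatigue (5) and diarrhea (4). Overlap and attribution are not given, and the counts show who might enter the row, not who would be dosed differently. In Appendix L (16.13), atrial fibrillation accounts for 110 of the 130 listed serious cardiac reactions (110 + 14 + 4 + 2), or 85%, but that is a share. Against all exposed subjects it is 110/4791 = 2.3%, of unstated grade and from a pooled population.

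Nor does the point touch the two-stage response-rate design. It should be corrected because it concerns safety and costs little.

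**What to change.** Amend section 3.3.2 as follows.

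1. State that the required-reduction list and the table take precedence, and that 3.3.2.1 applies only to events meeting neither.
2. State that the table's cardiac discontinuation rows override both the list's catch-all item and 3.3.2.2.
3. Write the table's restart steps as dose levels below the dose at onset, so that they work for participants starting at 280 mg or 140 mg.
4. State the action when an event occurs at 140 mg.

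Two related matters are clinical choices that the precedence wording need not decide: whether further event types join the table's last row, and whether different toxicities count together as occurrences.

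The cost is a wording amendment to one section, with no added visits or procedures. The downside is that some participants would be reduced or stopped one occurrence earlier than 3.3.2.1 would allow, and earlier still under the cardiac rows.

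### Section 3.3.2 restarts at fixed doses that give a participant already on 280 mg no reduction at a first event, and its table conflicts with 3.3.2.1 with no rule on which governs

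*Combined protocol and SAP*

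**What the plan says.** The standard dose is 420 mg daily (Section 3.2). Section 3.2.1 lowers it to 280 mg with voriconazole or lower-dose posaconazole, and to 140 mg with higher-dose posaconazole.

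Section 3.3.2 then gives two sets of instructions. The first is a mandatory list, introduced by "Dose reductions will be required for any of the following toxicities", which includes the catch-all "Any other Grade 4 or unmanageable Grade 3 toxicity attributed to ibrutinib". The second is a table titled "Recommended Dosage Modifications for Adverse Reactions". Its last row covers "Other Grade 3 or 4 non-hematological toxicities", "Grade 3 or 4 neutropenia with infection or fever" and Grade 4 hematological toxicities. For that row the first event is "Restart at 280 mg daily", the second is 140 mg and the third is discontinuation. Grade 2 cardiac failure has the same sequence. Grade 3 arrhythmia restarts at 280 mg and stops at the second event. No footnote addresses a participant who is already below 420 mg.

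Section 3.3.2.1, titled as general rules, has no grade limits. After a first hematologic event the participant "may restart at the original dose level", and after a first non-hematological event "may restart at original dose level". The second and third events each step down one level, and the fourth is discontinuation.

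The hepatic rules (Section 3.3.2.3 and its Table 1) are already relative: they restart one level below the dose at which the toxicity occurred.

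**The concern.** These rules set the dose after a severe toxicity, and such events are to be expected. Section 1.2.2.3 reports that among 42 patients with steroid-refractory chronic GvHD, Grade 3 or higher pneumonia occurred in 6, fatigue in 5 and diarrhea in 4.

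There are two separate faults. First, the fixed restart doses make sense only for someone taking 420 mg. A participant whose dose was already lowered for an azole gets no reduction or no usable instruction. If the toxicity is on the mandatory list, the table contradicts that list within the same section. Second, for a 420 mg participant with an event off the mandatory list, one site can restart at 280 mg and another at 420 mg. They can also stop treatment one event apart, and both would be following the protocol.

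**Working it through.** The plan gives no figure to reproduce. The check applies each table to each dose that Section 3.2.1 allows.

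**Fixed doses: last row of the 3.3.2 table**

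Change at an event = (restart dose − current dose) / current dose.

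| Dose at first event | Event 1 | Event 2 | Event 3 |
|---|---|---|---|
| 420 mg | 280 mg: (280 − 420)/420 = −33% | 140 mg: (140 − 280)/280 = −50% | stop |
| 280 mg | 280 mg: (280 − 280)/280 = 0% | 140 mg: (140 − 280)/280 = −50% | stop |
| 140 mg | literal cell 280 mg, above the current dose | 140 mg, no lower than the starting point | stop |

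At 280 mg the first reduction comes at event 2, one event late. At 140 mg the literal increase is plainly unintended, but setting it aside leaves no instruction, and no dose below 140 mg is reached before the stop.

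**Two tables: 420 mg participant, event off the mandatory list**

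The catch-all reaches Grade 4 and unmanageable Grade 3 toxicity. These events are therefore in the 3.3.2 table but not clearly on the list:
- manageable Grade 3 non-hematological toxicity
- Grade 2 cardiac failure
- Grade 3 neutropenia with infection but no temperature of 38.5 °C or more

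| Event | 3.3.2 table | 3.3.2.1 |
|---|---|---|
| 1 | 280 mg | 420 mg permitted |
| 2 | 140 mg | 280 mg |
| 3 | stop | 140 mg |
| 4 | not reached | stop |

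The tables are one step apart at each of the first three events, and the stop is at event 3 or event 4. For a manageable Grade 3 arrhythmia the gap is wider, with the stop at event 2 or event 4. Atrial fibrillation is left aside because it has its own text in 3.3.2.2.

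For events on the mandatory list, the required reduction overrides the permission in 3.3.2.1, so no first-event conflict between the two tables is claimed there.

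**Not affected.** The rows that discontinue at the first event, and the hepatic rules.

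**Related gap.** When the inhibitor stops, Section 3.2.1 allows a return to 420 mg and Section 14.1.7 advises it. Neither says that only the inhibitor adjustment is reversed, so a toxicity reduction could be undone without the 4-week no-recurrence condition in 3.3.2.

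**The case against.** The strongest reply on the fixed doses is that a mandatory reduction outranks a table titled as a recommendation. A listed toxicity at 280 mg must then lead to 140 mg, since the Précis names only 280 mg and 140 mg as reduced doses and both 3.3.2.1 and Table 1 spell out the step from 280 to 140 mg. That is a sensible way to rescue the text, and it narrows the harm for listed events. It also concedes that the table's cell is wrong for those participants. It does not settle off-list events at 280 mg, or any event at 140 mg.

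On the two tables, one can argue that the specific governs the general, and that restarting at 280 mg and stopping at the third event breaches neither, because 3.3.2.1 only permits the higher dose. This is the natural reading for Grade 2 cardiac failure, which has its own row. It is weaker for the row on other Grade 3 or 4 non-hematological toxicities, which is itself general. No sentence states precedence, and a site that follows 3.3.2.1 is also compliant.

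The azole group may be very small. Exclusion 2.1.2.7 removes users of strong CYP3A inhibitors, the wording of 3.2.1 suggests that these azoles count as strong, and Section 4.3 names isavuconazole first for prophylaxis. Against that, Appendix C does not class voriconazole as strong and does not list posaconazole, Section 3.2.1 gives doses for both, and an azole may be started after entry.

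Optional reduction at investigator discretion, the benefit-risk footnotes, and the weekly meetings and principal investigator review in Section 7.5.1 all lower the risk. None of them states the dose.

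**Conclusion.** The concern holds. Followed as written, the 3.3.2 table gives 0% reduction at a first event for a participant on 280 mg and no usable dose for one on 140 mg. For off-list events in a 420 mg participant, 3.3.2 and 3.3.2.1 differ by one dose step at each of the first three events and by at least one event in when to stop, with no rule between them.

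The first part assumes that some participants take voriconazole or posaconazole during treatment. Their number is unknown and probably small. The second part needs no such assumption, but the documents give no rate for off-list events, so no count is claimed. The consequence is for participant safety and for consistency of dosing between sites; the two-stage design and its error rates are not touched. This should be fixed, and confidence is high.

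**What to change.** - Word the 3.3.2 restart column as one dose level below the dose at which the toxicity occurred, as Table 1 already does.
- State the action for an event at 140 mg: discontinue, or change the azole.
- State that the 3.3.2 list and table together govern over 3.3.2.1 for the toxicities they name. This sentence should make the table's doses binding, because its title leaves them advisory.
- State in 3.2.1 and 14.1.7 that stopping the inhibitor reverses only the inhibitor adjustment, and that a toxicity reduction is reversed only under the 4-week no-recurrence condition in 3.3.2.

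The cost is one amendment to a table column and a few sentences, with no added visits, tests or participants. The 3.3.2 ladder from 420 mg stays at 280 mg, 140 mg, stop. The downside falls on azole-treated participants. If the action at 140 mg is to discontinue, someone starting at 280 mg stops at event 2 (140 mg, stop) and someone at 140 mg stops at event 1, instead of event 3 for both. Changing the azole avoids this.

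### The restart doses in the section 3.3.2 table are absolute and clash with the reduced doses in section 3.2.1; section 3.3.2.1 adds a permission with no grade limit or precedence rule

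*Combined protocol and SAP*

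**What the plan says.** Section 3.3.2 opens its list with "Dose reductions will be required for any of the following toxicities". The list includes Grade 4 thrombocytopenia, Grade 3 thrombocytopenia "in the presence of clinically significant bleeding events", and "Any other Grade 4 or unmanageable Grade 3 toxicity attributed to ibrutinib".

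The table below it is headed as recommended modifications. For "Other Grade 3 or 4 non-hematological toxicities", for "Grade 4 hematological toxicities" and for Grade 3 or 4 neutropenia with infection or fever, it gives 280 mg after the first event, 140 mg after the second and discontinuation at the third. Grade 2 cardiac failure follows the same steps. Grade 3 arrhythmia restarts at 280 mg once and is then discontinued. No row refers to the dose being taken when the toxicity occurred. A closing sentence says the dose "may be re-escalated after 4 weeks of a dose reduction in the absence of a recurrence of the toxicity that led to the reduction", at the investigator's discretion and with no stated ceiling.

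Section 3.3.2.1, titled as general, gives a second schedule. For a first hematologic event it reads: "Withhold ibrutinib until recovery to Grade ≤ 1 or baseline; may restart at the original dose level". The non-hematologic rows say the same. Later events go down one level from the dose at which the toxicity occurred, and the drug stops at the fourth. No triggering grade is named; the recovery target implies Grade 2 or above but sets no upper limit.

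Section 3.2.1 assigns 280 mg once daily with voriconazole at any dose or posaconazole suspension up to 200 mg twice daily, and 140 mg with the higher posaconazole doses. It allows an increase to 420 mg if those drugs are later stopped.

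**The concern.** The table works only for a participant taking 420 mg. For someone already at 280 or 140 mg because of an antifungal, a fixed restart dose may be no reduction at all, or an increase, after a toxicity for which the same section requires a reduction. The protocol's other schedules avoid this: hepatic Table 1 in section 3.3.2.3 steps down from the dose at which the toxicity occurred, starting with the first event, and section 3.3.2.1 does so from the second.

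Separately, section 3.3.2.1 overlaps both the list and the table and permits the full previous dose where they call for less. One listed toxicity, Grade 3 thrombocytopenia with significant bleeding, has no row in the 3.3.2 table unless the bleed itself is Grade 3 or 4. The only occurrence schedule left for it is the permissive one.

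At stake are participant safety and uniform dosing across sites. Exposure matters here: section 1.2.2.2 reports an exposure-response relationship in Study MCL3002 for atrial fibrillation and for any hemorrhage, although that does not measure the risk in this trial.

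**Working it through.** The plan gives no figure to reproduce on this point. The check applies each rule to each dose level.

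Inputs:
- dose levels of 420, 280 and 140 mg, with none lower (Précis, Design)
- table restart doses of 280 mg, then 140 mg (section 3.3.2)
- original dose at the first event, one level down at the second (section 3.3.2.1)
- doses with antifungals (section 3.2.1)

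Change = (restart dose − current dose) / current dose. The example is Grade 4 thrombocytopenia, which is on the required list, in the table and within the scope of section 3.3.2.1.

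| Current dose | Event | 3.3.2 table | Change under table | 3.3.2.1 allows |
|---|---|---|---|---|
| 420 mg | first | 280 mg | (280 − 420)/420 = −33% | 420 mg |
| 280 mg | first | 280 mg | (280 − 280)/280 = 0% | 280 mg |
| 140 mg | first | 280 mg | (280 − 140)/140 = +100% | 140 mg |
| 420 mg (after re-escalation) | second | 140 mg | (140 − 420)/420 = −67% | 280 mg |
| 280 mg | second | 140 mg | (140 − 280)/280 = −50% | 140 mg |
| 140 mg | second | 140 mg | (140 − 140)/140 = 0% | no lower level defined |

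Three of the six table cells fail to reduce the dose, and one of those raises it. At a first event, section 3.3.2.1 permits no reduction at any dose level.

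The proposed rule is restart dose = min(table dose, one level below the current dose):
- 420 mg, first event: min(280, 280) = 280 mg
- 420 mg after re-escalation, second event: min(140, 280) = 140 mg
- 280 mg, first event: min(280, 140) = 140 mg
- 280 mg, second event: min(140, 140) = 140 mg
- 140 mg: no lower level, so an explicit action has to be written

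The sequence for a participant starting at 420 mg (280, 140, stop) is unchanged.

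Whether participants at 280 or 140 mg will exist can be judged only from the text. In favor: section 3.2.1 gives them doses, Appendix C lists neither voriconazole nor posaconazole as a strong inhibitor, and section 4.3 recommends isavuconazole or an alternate agent above 0.20 mg/kg prednisone equivalent, while section 2.1.2.3 admits participants on up to 0.5 mg/kg. Against: section 2.1.2.7 excludes recent or continuous use of strong CYP3A inhibitors, section 14.1.7 says to avoid them, and the wording of the last row in the section 3.2.1 table suggests that both drugs count as strong. Such participants are foreseeable; their number is not given.

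**The case against.** A reader might infer that the protocol orders a doubled dose for participants on posaconazole. It does not. The table is headed as a recommendation, the sentence above it makes reductions mandatory for the listed toxicities, and section 3.2.1 allows a rise only when the antifungal is stopped. Moving from 140 to 280 mg on continuing posaconazole would breach both. The same reasoning applies to section 3.3.2.1: it says may, and a permission yields to a requirement. Weekly team review of each participant (section 7.5.1) is a further safeguard. All of this stands, but it means that an investigator must override the table to dose correctly, and no text says so.

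The gap for Grade 3 thrombocytopenia is also narrow. Section 8.1.6.1 has bleeds that need red-cell transfusion reported as Grade 3 or higher, which brings them under the non-hematological row. What remains is clinically significant bleeding below Grade 3.

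Three further readings are tempting and not supported:
- The list and the table differ on Grade 3 non-hematological toxicity and on how long Grade 4 neutropenia must last. A mandatory minimum and a broader recommendation can coexist.
- Section 3.3.2.2 asks for a risk-benefit judgment in Grade 4 atrial fibrillation, while the table discontinues for "Grade 4 cardiac arrhythmias". Section 1.2.2.4.5 says to weigh risks and benefits and also to follow the dose guidelines, so the table is not displaced.
- The missed-dose rules in sections 3.2, 3.3.2.3 and 3.8.1 are worded differently, but applying the stricter one satisfies all of them.

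These three call for editorial alignment only.

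**Conclusion.** The point holds as a conflict between dosing rules. Followed literally, the 3.3.2 table gives a 0% reduction at 280 mg and a 100% increase at 140 mg after a first event, and a 0% reduction at 140 mg after a second. Section 3.3.2.1 permits the original dose after first events for which section 3.3.2 requires less, and nothing states which prevails. The sensible reading is that the required-reduction sentence and the section 3.2.1 dose govern.

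The conclusion assumes that some participants will take voriconazole or posaconazole, which the protocol provides for but does not quantify. It concerns safety and consistency of dosing; no effect on the 6-month response rate or on the two-stage design is claimed. The wording gap is certain, and how often it would matter is unknown. It ranks between a minor point and one that should be fixed.

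**What to change.** 1. In the 3.3.2 table, restart at the lower of the table dose and one level below the dose at which the toxicity occurred. Never exceed the dose that section 3.2.1 assigns, including on re-escalation.
2. For a participant already at 140 mg, hold the drug and do not restart above 140 mg. The sponsor should choose between discontinuation and a documented benefit-risk decision, for example after a change of antifungal. Automatic discontinuation is not proposed: it would stop such a participant at a first event, where one at 420 mg has two reductions available.
3. State that the section 3.3.2 list and table override section 3.3.2.1, which then applies only to events outside both.
4. Add a table row for Grade 3 thrombocytopenia with clinically significant bleeding.

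The list and table wording, the atrial fibrillation cross-reference and the missed-dose wording can be aligned in the same amendment.

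The cost is one protocol amendment with IRB review and a clinical decision on the 140 mg case, with no new visits or procedures. The downside is that some participants on antifungals may be reduced or stopped earlier than under the present table.
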